1.0 Objectives / Specific Aims

Aim 1. Assess whether the parasympathetic effects of transcutaneous auricular vagus nerve stimulation (taVNS) are able to attenuate the sympathetic response curve elicited by a validated cold pressor test.

We will recruit 24 neurotypical subjects (ages 18-65) in order to have at least 14 completers. The subjects must be at baseline healthy, and not have a history of major mental or medical illness (see more below for full inclusion/exclusion criteria). Each subject will undergo phone screen and be consented prior to participating in the study. Each subject will participate in 1 study visit, where they will participate twice in the validated cold pressor test while concurrently receiving active or sham taVNS. Subjects will participate in both treatment conditions (active and sham taVNS), however the order in which they participate will be randomized (half will receive active taVNS first, half will receive sham first). The cold pressor test is a validated stress induction technique and has been shown to produce a reliable sympathetic response, as shown by acute elevations in sympathetic physiologic markers (heart rate, blood pressure/mean arterial pressure, cardiac output, etc). In prior studies, taVNS has been shown to produce a marked and significant parasympathetic response in neurotypical subjects, shown by acute reductions in the same markers as above. Both taVNS and the validated cold pressor test have been shown to be safe and feasible in neurotypical subjects. We hypothesize that subjects receiving active taVNS will have an attenuated sympathetic response to the cold pressor test compared to those receiving sham stimulation.

Aim 2. Assess whether taVNS affects the subjective pain/stress response to a validated cold pressor test.

Subjects will be asked to rate subjective pain and stress before, during, and after the cold pressor test. We hypothesize that these subjective ratings will be reduced in the group receiving active taVNS compared to the sham group.

Aim 3. Assess the acute effects of transcutaneous auricular vagus nerve stimulation (taVNS) on anxiety.

In other pilot trials using taVNS, as well as past trials with implanted VNS, results have shown taVNS and implanted VNS to have an anxiolytic effect. We hypothesize that taVNS will have a similar anxiolytic effect on subjects in this trial. This work will provide pilot data for subsequent studies to investigate the anxiolytic effects of taVNS.

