3.0 Intervention to be studied

The intervention we are studying is called transcutaneous auricular vagus nerve stimulation (taVNS). taVNS is simply electrical nerve stimulation administered at the ear which targets the auricular branch of the vagus nerve. taVNS will be administered using the Digitimer DS7a nerve stimulation system that has an FDA 510k approval. taVNS is a non-significant risk method that has been approved by the MUSC IRB for many ongoing taVNS trials.

The Digitimer DS7a manual has been uploaded the MUSC IRB portal and can be found here: <https://www.digitimer.com/product/human-neurophysiology/peripheral-stimulators/ds7a-ds7ah-hv-current-stimulator/>

- Cervical VNS is FDA approved for medication resistant epilepsy as well as medication resistant depression (Livanova). FDA pivotal trials are underway for paired cervical VNS with rehab for stroke (microtransponder). Noninvasive cervical VNS is FDA approved for treating cluster headache (electrocore). To date there are no FDA approved indications for taVNS.
- We will use the device during each study visit for up to 5 minutes while subjects concurrently participate in the cold pressor test. Subjects will receive both stimulation conditions over the course of the study visit (active taVNS x1, sham taVNS x1). Subjects will be blinded to stimulation condition, but the research team will know whether patients are receiving active or sham stimulation. The order in which subjects receive either active or sham stimulation will be randomized (half will receive active taVNS first, half will receive sham taVNS first).

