4.0 Study Endpoints

Outcomes will include vital signs, and ratings of anxiety, pain, and stress. Over the course of the study visit, physiological measures will be collected before, during, and after a cold pressor test (more about data collection below). Visual analog measures of anxiety, stress, and pain will be collected throughout each study visit.

Primary Outcome:

Given that safety and feasibility of taVNS and this intervention have already been established by prior studies, the primary outcomes in this study will be the physiological measures collected at each study visit (Badran, 2019). Both taVNS and the validated cold pressor test have been shown to be safe and feasible in neurotypical subjects (Badran 2018a, b, c; Lovallo, 1975). Biopac equipment will be used to continuously measure heart rate/variability (HRV) and blood pressure to assess autonomic responses.

Secondary Outcome:

Subjective measures of pain, stress, and anxiety will also be collected before, during, and after the cold pressor test (with concurrent taVNS). These will be measured using visual analog scales. Baseline measures of anxiety and mood will also be collected at the initial visit.

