Timeline consists of 2 cold pressor tests (CPT) and 2 stimulation conditions (active and sham). The cold pressor test (CPT) will last for up to 3 minutes. Subjects will receive either active or sham taVNS for up to 5 minutes (stimulation will start prior to CPT and continue throughout the duration of the CPT). The order in which participants receive active or sham taVNS will be randomized, but all participants will receive both treatment conditions. Physiologic data will be continuously measured throughout the course of each visit.

Cold Pressor Test: The CPT was first introduced in the 1930s by Hines and Brown (Hines, 1932). CPT exposure leads to profound changes in cardiovascular parameters most notably a rise in blood pressure throughout peripheral vasoconstriction and to a lesser extent cardiac output resulting from an increase in both vascular alpha-adrenergic and cardiac beta-adrenergic drive (Greene et al., 1965; Lollo, 1975; Yamamoto et al., 1992). On the subjective level participants experience the CPT as painful and report heightened levels of perceived stress and arousal during and immediately after the water-bath (Zoladz et al., 2014). A plethora of research has contributed to the validation and standardization of the CPT.

Prior studies have shown an enhanced response, in terms of sympathetic parameters, to a bilateral feet CPT (Larra, 2015). This is what will be used in this trial. As in previous studies (Larra, 2015; Bachman, 2018), the CPT will consist of participants immersing both feet into ice-water (water temperature around 2-3 degrees Celsius) for up to 3 minutes. The water-bath will be a rectangular tub with ample volume to submerge the subject's feet completely with ice-water.

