Upon arrival, subjects will be asked to sit comfortably in a chair as electrodes are applied to collect physiological data (see physiology section below). The protocol will start with a resting period during which heart rate and blood pressure will be assessed. Subjects will receive a 2-minute warning prior to the start of the CPT. Subjects will be asked to rate subjective anxiety, stress, and pain during this resting period. After the resting period, subjects will be exposed to the CPT for up to 3 minutes. During the exposure to the ice water, subjects will again rate subjective anxiety, stress, and pain. The stress procedure will be followed by another resting period, during which heart rate and blood pressure will continue to be monitored. Again, participants will rate subjective anxiety, stress, and pain.

taVNS: The taVNS stimulation administered during the study *is non-invasive but includes some risk*. Participants will be screened for potential contraindications to taVNS prior to invitation to the lab (see Section 5.0 for exclusion criteria; e.g., ear trauma/pain, metal implants). The device has safety mechanisms to prevent electrical surges. Skin will be prepared using 70% alcohol swabs prior to electrode attachment to ensure sanitation and stimulation power is safe. Metal jewelry also will be removed from the head. Stimulation is applied using electrodes and a water based conductive gel, and participants will be assessed after application/prior to stimulation for discomfort related to the electrode. Participants will be assessed during stimulation for discomfort or adverse events over the course of stimulation, though

studies have demonstrated few concerns of safety. Participants are encouraged to share report of discomfort and are reminded prior to the study they may discontinue at any point. The ear also will be cleaned and inspected for irritation/redness after stimulation. The ear stimulation delivered during the study includes some risk. Participants in previous research using this stimulation describe the feeling as a “tickle” or “pricking” sensation. Some report mild irritation. Our researchers will inspect the ear after stimulation given previous research has documented some redness from the stimulation.

Physiology: For sensors that are attached to skin there is some risk for mild local irritation or redness, thus adhesives are removed with caution/gently.

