13.0 Provisions to Monitor the Data to Ensure the Safety of Subjects

The PI and co-Is will be responsible for monitoring the data collection and safety of participants. This study involves some risk, though previous research at MUSC using the same stimulation parameters has demonstrated no major or minor adverse events during or after stimulation when assessing skin discomfort, irritation, headache, facial pain and dizziness, heart rate, respiration, and self-reported pain (Badran et al., 2018). Researchers identified redness at stimulation location and pain ratings in this study were means of 2.1 and 1.2 (out of 10) for the tragus and the ear lobe, respectively. Brain Stimulation Lab physicians will be readily available should adverse events occur.

The questionnaire, experimental, and physiological data will be monitored to ensure the safety of subjects. During the study participants will be inquired about their comfort with regard to the stimulation and will be informed (prior to stimulation) that they may terminate at any point. Participants will be assessed for adverse events in the current study, including skin discomfort, irritation, headache, facial pain and dizziness.

Quality Control: Regular data verification meetings will take place weekly with the PI, co-Is, and the study personnel to ensure proper procedures are followed (consenting, data collection and de-identification), ensure study/experimental protocol adherence, and to assess for adverse events. In addition, study personnel will be trained to contact the PI immediately, in the case of an adverse event. Events determined by the PI to be unanticipated problems involving risks to subjects or others, or to be an adverse event, in accordance with HRPP guideline 4.7, will be reported by the PI to the IRB as soon as possible and after no later than 10 working days, per IRB policy described in guideline 4.7.

Access & Safety Training: Research staff assisting with physiological data collection will receive first aid and CPR certification to assess and respond to participant emergencies during the study. The PI and Co-I each have expertise in physiological and clinical data collection and will be responsible for training any additional research staff in proper procedures for sensor use/ placement and handling of data.

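### The in-water pain rating names no body site and is taken while the ear is being stimulated, so Aim 2's cold-pain score may also contain ear pain

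*Protocol*

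**What the plan says.** Protocol Section 1.0 sets Aim 2 as "Assess whether taVNS affects the subjective pain/stress response to a validated cold pressor test" and gives the expected direction: "We hypothesize that these subjective ratings will be reduced in the group receiving active taVNS compared to the sham group".

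On the instrument, Section 4.0 says "These will be measured using visual analog scales". On timing, Section 10.0 has pain rated at rest beforehand, during immersion and at rest afterwards. For the rating that matters most it says "During the exposure to the ice water, subjects will again rate subjective anxiety, stress, and pain". Sections 1.0, 4.0 and 10.0 all call the item simply pain; none ties it to the feet, the water or the ear.

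Section 10.0 also says that "stimulation will start prior to CPT and continue throughout the duration of the CPT". The ear is therefore being stimulated when the in-water rating is given.

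Section 13.0 cites earlier work at the same institution, described as "previous research at MUSC using the same stimulation parameters has demonstrated no major or minor adverse events", and reports that "pain ratings in this study were means of 2.1 and 1.2 (out of 10) for the tragus and the ear lobe, respectively". Section 3.0 describes the intervention only as "taVNS is simply electrical nerve stimulation administered at the ear which targets the auricular branch of the vagus nerve". The text at hand does not say where on the ear active stimulation is applied, nor where or at what current sham is applied.

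Sections 10.0 and 13.0 provide for checks of discomfort during stimulation as part of tolerability and adverse-event monitoring. No ear pain score is specified.

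**The concern.** The quantity Aim 2 wants is the change in cold pain. The quantity the plan collects, as written, is pain at a moment when there are two possible sources: the feet in ice water and the electrode on the ear. If active and sham feel different at the ear, the active-sham contrast on that score is the effect on cold pain plus some part of the difference in ear pain.

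The crossover and the randomised order balance period effects. They do not balance a sensation that belongs to the condition, because it is present in every active period and absent, or different, in every sham period. No later analysis can recover the two components if only one undirected rating was taken. The point therefore belongs to data collection in the protocol rather than to the SAP.

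What is at stake is how the pain half of Aim 2 can be read. If active stimulation hurts more and this enters the score, a true reduction in cold pain would be understated, and a null result would be ambiguous between no effect and an effect offset by ear pain.

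**Working it through.** **Inputs from the protocol**
- Earlier mean stimulation pain: 2.1 (tragus) and 1.2 (ear lobe), out of 10, with no SD or sample size (Section 13.0).
- At least 14 completers out of 24 recruited (Section 6.0), each receiving both conditions.
- No alpha, power, SD or target difference for pain is given, so there is no figure of the plan's own to reproduce. Section 4.0 gives no range for the scale.

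**Step 1: size of the possible site difference**
- Tragus against ear lobe: 2.1 - 1.2 = 0.9 points.
- Same site and same current in both conditions: about 0.
- Tragus against a sham with no current: 2.1 - 0 = 2.1 points.

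The documents do not say which of these applies. The 0.9 is the difference between the two means that Section 13.0 reports.

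**Step 2: effect on the contrast**

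Let *d* be the true reduction in foot pain under active and *f* the fraction of the 0.9 points that enters the in-water score. Then

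observed reduction = *d* - *f* × 0.9.

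With *f* = 0 the ear is ignored; with *f* = 1 the two pains add fully. If the ear sensation distracts from the cold, *f* is in effect negative and the reduction is overstated. The documents give no basis for choosing *f*.

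**Step 3: illustration at the planned size**

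The assumptions here are mine, not the plan's: 0-10 scale, paired t-test, two-sided alpha 0.05, n = 14 (13 df, critical value 2.160), *d* = 1.5 points, SD of the within-subject difference 1.5 to 2.5. The noncentrality is (*d* - 0.9*f*)/SD × √14. For example, with SD 2.0 it is 1.5/2.0 × 3.742 = 2.81 at *f* = 0 and 1.05/2.0 × 3.742 = 1.96 at *f* = 0.5.

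| *f* | Observed reduction | Power, SD 1.5 | Power, SD 2.0 | Power, SD 2.5 |
|---|---|---|---|---|
| 0 | 1.500 | 93% | 74% | 55% |
| 0.25 | 1.275 | 84% | 60% | 42% |
| 0.5 | 1.050 | 68% | 44% | 31% |
| 1 | 0.600 | 28% | 18% | 13% |

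The reduction detectable with 80% power at n = 14 is 1.22, 1.63 and 2.03 points for SD 1.5, 2.0 and 2.5. The 0.9 points are 0.9/1.22 = 74%, 0.9/1.63 = 55% and 0.9/2.03 = 44% of these. The last row of the table is the extreme for the tragus-ear lobe case, not an expected result. Partial carry-over would still matter at this sample size; zero carry-over would cost nothing.

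**The case against.** **The wording may sit on the rating form.** The protocol need not print each scale item, and the surrounding text is about the cold pressor test, so subjects may in practice be asked about the cold. This stands in part: the form is not shown. But the item as the protocol describes it is generic, and a form built from that description would collect a generic rating.

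**The sites are not stated.** A reader might infer from Section 13.0 that active is at the tragus and sham at the ear lobe, and so that active is bound to hurt more. The documents do not support that. Section 3.0 says only that stimulation is at the ear, and the sham is not described. If both conditions feel alike, the problem disappears. This objection stands, and it is why the 0.9 is conditional.

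**Ear pain may not carry over.** Pain of about 2 out of 10 at the ear may be swamped by both feet in water at 2-3 degrees Celsius, or the ear sensation may distract. This also stands. The two means come from a passage about safety and say nothing about ratings given during immersion.

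**The pre-immersion rating may help.** Stimulation starts before immersion. If the resting rating is taken after onset, change from that rating would remove part of the ear component. Section 10.0 does not say whether stimulation is on at that rating, and the timeline figure is not shown, so this remains open.

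**Any bias would be conservative.** This is true only if ear pain adds to the score and is greater under active. Under distraction the sign reverses, so the argument does not settle the matter.

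**Conclusion.** The point holds as a measurement risk, not as a demonstrated bias. As the protocol describes it, one undirected pain score is taken while both possible pain sources are present. The protocol's own figures show that stimulation pain can differ by site, and nothing in the planned data would allow the two to be separated.

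The illustrative size is up to about 0.9 points out of 10 in the active-sham contrast. This assumes that the conditions differ as tragus and ear lobe do, that the earlier means apply here, and that ear pain adds fully. The real amount is unknown, may be nil, and may have the opposite sign.

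Two stronger readings are tempting and are not supported. One is that a null result on pain could not be interpreted at all; it would be ambiguous, which is less. The other is that the stress rating is affected in the same way; the documents give no figure for stress caused by stimulation, and stress has no body site to specify. The point concerns the pain rating only, which is a secondary outcome in a pilot project. It is a cheap improvement rather than a flaw that undermines the trial.

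**What to change.** In Sections 4.0 and 10.0 of the protocol, word the pain scale as *pain in your feet from the cold water* and name that item as the pain outcome for Aim 2. At the same time points and in both conditions, add one line, *pain or discomfort at the ear*, on the same type of scale, and report it separately as an effect of stimulation.

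Leave the existing discomfort and adverse-event checks unchanged. They cover more than ear pain (headache, facial pain and dizziness among others), and a one-line scale does not replace them.

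The cost is a reworded item, one extra line on the form and a few seconds per rating. The extra line draws slightly more attention to the stimulation in subjects who are meant to be blinded to condition; asking it after the foot rating limits this. The change will not remove a genuine distraction effect on foot pain, but the ear score would show how far the two conditions differ in sensation and so help in reading the result.

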12.0 Data Management

Analyses: The psychophysiological data will be processed using standard protocols which have previously been used in this lab and in various other studies (Sege et al., 2017, 2018, Taylor et al., 2020), and according to published guidelines (Blumenthal et al., 2005; Boucsein et al., 2012; Gatchel et al., 1973; Keil et al., 2014).

Telephone screening information will be stored in a locked filing cabinet in the Brain Stimulation Lab, along with each participant’s signed informed consent. Data regarding subject’s ratings of subjective anxiety/stress/pain will be stored in the Redcap database. Information about the participant (including their identifiable private information and/or any identifiable biospecimens) may have all of their identifiers removed and used for future research studies or distributed to other researchers for future research without additional informed consent from them or their legally authorized representative.

Confidentiality and Quality Control: All study personnel will complete Social-Behavioral-Educational research CITI training, and also complete in-lab training regarding data security practices. Study personnel will be trained in the IRB protocol. The investigator, and co-investigators will be available to monitor data collection to ensure quality, confidentiality, and adherence to the IRB protocol.

The majority of this study’s procedures will take place in the study’s research suite, which is a private room with limited access. Regarding documentation, participant names will appear only on the IRB-approved Consent, HIPAA, and payment forms. It cannot be guaranteed that participants will complete these study portions in private spaces, though they will be encouraged to do so for their protection. Payment forms will be collected and stored separately from data in a locked cabinet for up to 6 years.

After participation, RedCAP data will be downloaded in excel format to the secure MUSC server. Finally, physiology data files will also be linked only to participant code; these data will be transferred to an MUSC Box account that is only linked to the participant’s code.

In terms of publication, data will be published in aggregate form, so individual participants will not be identifiable in the final manuscript. No identifying information will be published.

13.0 Provisions to Monitor the Data to Ensure the Safety of Subjects

The PI and co-Is will be responsible for monitoring the data collection and safety of participants. This study involves some risk, though previous research at MUSC using the same stimulation parameters has demonstrated no major or minor adverse events during or after stimulation when assessing skin discomfort, irritation, headache, facial pain and dizziness, heart rate, respiration, and self-reported pain (Badran et al., 2018). Researchers identified redness at stimulation location and pain ratings in this study were means of 2.1 and 1.2 (out of 10) for the tragus and the ear lobe, respectively. Brain Stimulation Lab physicians will be readily available should adverse events occur.

The questionnaire, experimental, and physiological data will be monitored to ensure the safety of subjects. During the study participants will be inquired about their comfort with regard to the stimulation and will be informed (prior to stimulation) that they may terminate at any point. Participants will be assessed for adverse events in the current study, including skin discomfort, irritation, headache, facial pain and dizziness.

Quality Control: Regular data verification meetings will take place weekly with the PI, co-Is, and the study personnel to ensure proper procedures are followed (consenting, data collection and de-identification), ensure study/experimental protocol adherence, and to assess for adverse events. In addition, study personnel will be trained to contact the PI immediately, in the case of an adverse event. Events determined by the PI to be unanticipated problems involving risks to subjects or others, or to be an adverse event, in accordance with HRPP guideline 4.7, will be reported by the PI to the IRB as soon as possible and after no later than 10 working days, per IRB policy described in guideline 4.7.

Access & Safety Training: Research staff assisting with physiological data collection will receive first aid and CPR certification to assess and respond to participant emergencies during the study. The PI and Co-I each have expertise in physiological and clinical data collection and will be responsible for training any additional research staff in proper procedures for sensor use/ placement and handling of data.

